7.1.7 Double-blind Intent-to-Treat Population

The DB ITT population will consist of all patients in the DB safety population who had at least 1 post-randomization assessment of the YMRS, MADRS, or CGI-S scores during the DB period of the study.

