6.7 DOUBLE-BLIND INTENT-TO-TREAT POPULATION

The DB ITT Population will consist of all who took at least 1 dose of DB IP and had at least 1 post-randomization assessment of the YMRS, MADRS, or CGI-S scores during the DBTP of the study, or had a relapse event.

Patients will be included in the randomized treatment group for the DB ITT population.

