10.0 EFFICACY ANALYSES

All efficacy analyses for the OLTP will be performed using the OL ITT Population, unless stated otherwise. Baselines for efficacy parameters in the OLTP will be defined as the last nonmissing efficacy assessment before the first dose of OL IP.

All efficacy analyses for the DBTP will be performed using the DB ITT Population, unless stated otherwise. Baselines for the additional efficacy parameters in the DBTP will be defined as the last nonmissing efficacy assessment before the first dose of DB IP.

All statistical tests will be 2-sided hypothesis tests performed at the 5% level of significance and all confidence intervals (CIs) will be 2-sided 95% CIs, unless stated otherwise.

To accommodate the flexible duration of the OLTP, the derived visits in the DBTP will be named as Week *i* post randomization (or DB Week *i*) for a specific Week *i* after the first dose of the DB study medications. The total exposure to IPs for patients in Week *i* post randomization will vary because of the flexible OLTP. The detailed week-mapping windows is provided in Section 16.1.

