The hypothesis testing will compare the time to relapse between each cariprazine group and placebo group using the log-rank test stratified by modified index episode (manic or depressive) and region (US, non-US) for the DB ITT population. To derive the modified index episode, the manic index episode(s) with or without mixed features will be classified as manic episode(s); depressive index episode(s) with or without mixed features will be classified as depressive episode(s). Estimates of the hazard ratio (HR) and 95% confidence intervals will be based on the Cox proportional hazards model with treatment group as the covariate stratified by modified index episode (manic or depressive) and region (US, non-US). The Kaplan-Meier estimates for the cumulative distribution of the relapse rate for each treatment group will be provided.

Per the protocol, relapses are collected within a double-blind treatment period that lasts with a maximum of 39 weeks (or 273 days + 3 days visit time window), hence all survival analyses will censor data at 276 days.

The primary hypotheses for cariprazine 3.0 mg/d and 1.5 mg/d treatment groups versus placebo will be tested sequentially in order to control the overall Type I error rate. The comparison of cariprazine 3.0 mg/d versus placebo will be tested first at two-sided 0.05 significance level, and only when it is significant, the comparison of cariprazine 1.5 mg/d versus placebo will be tested also at the two-sided 0.05 significance level. This testing strategy controls the overall Type I error rate at 0.05 significance level.

Two sensitivity analyses will be performed to assess the robustness of the primary analysis results to the possible violation of the noninformative censoring assumption.

The first sensitivity analysis will be based on the delta-adjusted method examined by Zhao et al. (2014), which specifies that the hazard of having an event for subjects who discontinued before the time point is increased relative to the hazard for subjects who continued beyond the time point for the experimental treatment group. The delta-adjustment will be gradually increased from zero until reaching the tipping point when the statistical significance of the primary efficacy endpoint is overturned, and the plausibility of the magnitude of delta-adjustment needed for reaching the tipping point will be subject to clinical scrutiny.

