17.2 SAFETY AND OTHER EVALUATIONS

This section specifies analyses related to COVID-19 pandemic from the following aspects:

- Disposition
- Study visit (missing entire visit due to COVID-19 or missing assessments due to COVID-19)
- Protocol deviation
- Study drug disruption due to COVID-19

- TEAEs related with COVID-19 and supplemental signs and symptoms
- COVID-19 status (COVID-19 testing results or contact with a COVID-19 positive person)

OL Safety Population or DB Safety Population will be used for the planned analyses described above. The number of participants impacted by COVID-19 during the OLTP will be summarized overall and the number of participants impacted by COVID-19 during the DBTP will be summarized by treatment group and overall. In addition, the number of patients impacted by COVID-19 and their corresponding disposition status in the OLTP and DBTP will be summarized respectively.

The number of patients who missed at least one entire visit due to COVID-19 will be summarized overall for the OLTP and by treatment group and overall for the DBTP. Furthermore, the number of patients who missed at least one assessment due to COVID-19 will be summarized by assessment category (laboratory, C-SSRS, urine pregnancy test, vital signs, ECG, and ophthalmological assessments) and overall. Similar summaries will be provided by visit.

The number of patients with significant protocol deviation due to COVID-19 will be provided. The number of patients with study drug disruption due to COVID-19 will be provided as well. The number of participants with TEAEs related to coronavirus infection or coronavirus test positive will be provided. Supporting listings for the described analyses above will also be provided.

18.0**CHANGES TO ANALYSES SPECIFIED IN PROTOCOL**

1. The definition of the DB ITT population in this document Section 6.7 was updated and overwrites the one specified in the Protocol Amendment 5, and reads as follows:

The DB ITT Population will consist of all who took at least 1 dose of DB IP and had at least 1 post-randomization assessment of the YMRS, MADRS, or CGI-S scores during the DBTP of the study, or had a relapse event.

2. The cutoff for the Age group in the SAP Section 7.4 was updated from 55 to 45 years old, due to imbalance between <55 and >=55 years based on the blinded data review. Now it reads as:

- Age group (< 45 years, \geq 45 years).

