#2	Section 11.2	Added Table 11.2-3	Define criteria for treatment-emergent significant changes in lipids
#2	Section 14.0	Revised assumptions for sample size determination	To align with protocol Amendment #5
#2	Section 16.1	Added Table 16.1-2	Define analysis windows in OLTP for lab and waist circumference parameters
#2	Section 16.1	Added Table 16.1-3	Define analysis windows in OLTP for PSP
#2	Section 16.1	Added Table 16.1-4	Define analysis windows in OLTP for EPS
#2	Section 16.1	Added Table 16.1-6	Define analysis windows in DBTP for lab and waist circumference parameters
#2	Section 16.1	Added Table 16.1-7	Define analysis windows in DBTP for PSP
#2	Section 16.1	Added Table 16.1-8	Define analysis windows in DBTP for WPAI-BD
#2	Section 16.1	Added Table 16.1-9	Define analysis windows in DBTP for EPS
#2	Section 17.0	New section specifying analyses for evaluating the impact of COVID-19	Evaluate impact of COVID-19
#3	Section 6.7	Updated the DB ITT population definition by including patients with relapse event but no efficacy assessments.	To account for relapses during the double-blind treatment period for patients without any efficacy assessments.
#3	Sections 10.1 and 10.3 and SAS codes in Appendices	Added 'region' to the models.	The study was stratified by region as well.
#3	Section 10.1	Updated age cutoff from 55 to 45 years.	Due to imbalance of age categories for 55 cutoff based on blinded data review.
#3	Section 10.1	New sensitivity analysis of primary endpoint, censoring ongoing Russian and Ukrainian participants after 24Feb2022.	Due to Russian-Ukrainian conflict that began on 24Feb2022.
#3	Section 10.1	Added 2 Kaplan-Meier figures.	To explore data further.
#3	Section 12.0	Updated text in WPAI.	WPAI description was missing.

SAP Amendment	Section	Major Revision	Rationale
#3	Section 12.0	Removed “The medical resource utilization and health economics assessments will be specified in a separate prospective analysis plan. “	No longer the process. HEOR now is part of this SAP document.
#3	Section 16.3	[REDACTED]	[REDACTED]

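### Among dosed patients with no post-randomization rating, SAP 6.7 keeps only the relapsers in DB ITT: selection on the outcome, small in effect and free to remove

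*SAP*

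**What the plan says.** Protocol 7.1.7 limits DB ITT to dosed patients who "had at least 1 post-randomization assessment of the YMRS, MADRS, or CGI-S scores during the DB period of the study", whatever their outcome. SAP 6.7 (Amendment #3) requires a dose and that the patient "had at least 1 post-randomization assessment of the YMRS, MADRS, or CGI-S scores during the DBTP of the study, or had a relapse event". SAP 18.0 discloses the change, saying the definition "was updated and overwrites the one specified in the Protocol Amendment 5", and Appendix IV gives the reason: "To account for relapses during the double-blind treatment period for patients without any efficacy assessments".

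The set is used widely. SAP 10.0 states: "All efficacy analyses for the DBTP will be performed using the DB ITT Population, unless stated otherwise". The primary test in SAP 10.1 is the "log-rank test stratified by modified index episode (manic or depressive) and region (US, non-US) for the DB ITT population". SAP 10.3 uses DB ITT for time to early discontinuation for any reason, with relapse counted as a discontinuation. The sensitivity program in Appendix II also starts by selecting on the DB ITT flag. No efficacy analysis on all randomized or all dosed patients is specified.

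Two further rules matter. Under SAP 10.1 a relapse can be declared without a rating (psychiatric hospitalization, new medication for worsening mood, or investigator opinion), and patients without relapse are censored when they complete or discontinue the double-blind period.

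**The concern.** The added clause repairs the set for events but not for non-events. A dosed patient who leaves before any rating and does not relapse is excluded; an otherwise identical patient who relapses is included. That is selection on the outcome inside a set labelled ITT, and a time-to-event analysis does not need it, because the plan already has a censoring rule for such a patient.

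Four analyses are exposed: the primary log-rank and Cox analysis; crude relapse rates, whose denominator loses only non-relapsers; time to any-cause discontinuation, where the excluded patients would be among the earliest events; and the two multiple-imputation analyses, which exist to test assumptions about early dropouts yet never receive these ones.

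**Working it through.** **1. Membership of DB ITT for dosed patients (SAP 6.7)**

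| Post-randomization rating | Relapse | In DB ITT |
|---|---|---|
| yes | yes | yes |
| yes | no | yes |
| no | yes | yes |
| no | no | **no** |

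Among unrated patients inside the set, the relapse proportion is 100% by construction. The sentence can also be parsed as (dose and rating) or relapse. The last row is then unchanged, and a relapser with no double-blind dose would enter too.

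**2. The plan's design figures reproduce (inputs from SAP 14.0)**

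Inputs: placebo relapse 35% at Week 39, HR 0.42, dropout 26%, 126 per arm, two-sided 5%, 85% power.

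- Schoenfeld events per pairwise comparison: 48.
- Active relapse rate: 1 − 0.65^0.42 = 16.55%.
- Patients per arm: 48 / (0.35 + 0.1655) = 93.1; 93.1 / 0.74 = 125.8, i.e. 126.
- With exponential relapse and dropout, event probabilities are 0.3055 (placebo) and 0.1436 (active): 126 × (0.3055 + 2 × 0.1436) = 74.7, against the stated 75.

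**3. Ceiling on the number affected**

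The documents give no count of unrated patients. Visit 13, the first double-blind rating, is two weeks after randomization. Assuming a constant dropout hazard:

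- Hazard: −ln(0.74) / 39 = 0.00772 per week.
- Leaving before Visit 13: 126 × (1 − exp(−2 × 0.00772)) = 1.93 per arm; 3 × 1.93 = 5.8 in total, 1.5% of 378.
- If every Visit 13 fell at the end of its +3-day window (17 days): 126 × (1 − exp(−(17/7) × 0.00772)) = 2.3 per arm.

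This counts all early leavers. Only those who also lack an ET rating, and did not relapse, are excluded.

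**4. Primary test (simulation)**

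Set-up: 1,500 trials per scenario, 126 per arm, the relapse and dropout rates above, 30% of unrated patients relapsing (assumed), unstratified log-rank, one-step HR. It compares all dosed patients with the SAP set.

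| True HR | Unrated, placebo / active | HR, all dosed | HR, SAP set | Rejection, all dosed | Rejection, SAP set |
|---|---|---|---|---|---|
| 1 | 2% / 2% | 1.012 | 1.012 | 4.9% | 4.8% |
| 1 | 5% / 5% | 1.015 | 1.015 | 4.6% | 4.6% |
| 1 | 10% / 10% | 1.005 | 1.005 | 4.9% | 5.0% |
| 1 | 10% / 2% | 0.927 | 0.926 | 5.8% | 5.8% |
| 1 | 2% / 10% | 1.086 | 1.088 | 7.5% | 7.5% |
| 0.42 | 2% / 2% | 0.440 | 0.440 | 86.7% | 86.7% |
| 0.42 | 5% / 5% | 0.454 | 0.454 | 84.6% | 84.6% |
| 0.42 | 10% / 10% | 0.477 | 0.477 | 77.7% | 77.9% |
| 0.42 | 10% / 2% | 0.405 | 0.404 | 92.5% | 92.6% |
| 0.42 | 2% / 10% | 0.518 | 0.520 | 70.0% | 69.4% |

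The largest differences are 0.002 in HR and 0.6 points in rejection. The unequal rows depart from the nominal HR in both sets, because those scenarios build in a real arm difference in early relapse.

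**5. Crude relapse proportion**

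With unrated share q, relapse share r among them, and event probability p among the rated:

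- All dosed: (1 − q)p + qr.
- SAP set: the same numerator divided by (1 − q) + qr.

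For placebo with q = 2% and r = 30%: 0.3054 against 0.3054 / 0.986 = 0.3097, up 0.4 points. Over q = 1–2% and r = 10–50%, the placebo rise is 0.2–0.6 points. At q = 10%, well above the ceiling in step 3, it is 1.7–2.8 points.

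**6. Time to any-cause discontinuation**

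Expected events per arm are 126 × (1 − 0.65 × 0.74) = 65.4 (placebo) and 126 × (1 − 0.65^0.42 × 0.74) = 48.2 (active). A loss of up to 1.9 is at most 1.93 / 65.4 = 3.0% and 1.93 / 48.2 = 4.0% of events, all in the first two weeks.

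**7. Imputation analyses**

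Applying the full 39-week rate to the ceiling, with no delta shift and φ = 0: 1.93 × 0.35 = 0.68 imputed events in placebo and 1.93 × 0.1655 = 0.32 per active arm. At φ = 1 the placebo rate applies to the active arms too (0.68). A positive delta raises the active figure further, but never above the 1.9 patients concerned.

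**The case against.** The strongest reply is that almost nobody is affected. Protocol 8.8 asks for a final assessment of every patient who took IP and discontinued, whatever the cause. Protocol 8.4.6 includes YMRS, MADRS and CGI-S in that visit, and SAP 7.1 places ET inside the double-blind period. Someone who leaves in week 1 with an ET rating is therefore in DB ITT. Protocol 12.13.2 requires the same scales at remote visits. This stands, and is why 1.9 is a ceiling and not an estimate. It does not prove the group empty: some patients will not return, and Protocol 12.13.5 omits efficacy ratings when ET procedures fall more than two weeks after the last dose.

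Second, the clause is a disclosed repair. The protocol set also lost unrated relapsers, so the SAP set is closer to all dosed patients than its predecessor, and SAP 7.1 reports population counts by arm, which will show how many are omitted. This stands too, but disclosure does not remove the dependence on outcome.

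A reader might infer that the primary hazard ratio is biased or its type I error inflated. Step 4 does not support that: excluded patients would be censored within about two weeks and carry almost no weight. A reader might also infer that the imputation analyses lose the patients they were built for. They do not: planned dropout is 0.26 × 126 = 32.8 per arm, so at least about 31 remain available for imputation.

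**Conclusion.** The point holds as a minor one. Among dosed, unrated patients, entry to the primary analysis set depends on relapse, and no other analysis in the plan covers those left out. The number is at most about 1.9 per arm if the planned 26% dropout is constant and Visit 13 is on schedule, and probably less given the ET ratings; front-loaded dropout would raise it.

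The primary test and hazard ratio are practically unaffected over the assumed range of 2–10% unrated. The real effects are a slight inflation of crude relapse rates, the loss of the earliest events from time to any-cause discontinuation, and fewer than about 0.7 (placebo) and 0.3 (each active arm) imputed events lost without a delta shift. The unrated share and the relapse share among the unrated are assumptions, because the documents state neither.

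**What to change.** For all time-to-event analyses and relapse rates, define DB ITT as all randomized patients who took at least one dose of double-blind IP, by randomized arm. Censor non-relapsers at discontinuation under the existing rule in SAP 10.1, using day 1 if there is no later date; a second censoring rule is not needed. Keep the condition of at least one rating only for the rating-scale analyses (MMRM and by-visit summaries), with its own flag. The same wording removes the and/or ambiguity in SAP 6.7. SAP 18.0 and the flag used in Appendix II should be brought into line.

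The cost is SAP text and one additional population flag, preferably before unblinding; no new data are needed. If the primary set is to stay as it is, running the same analyses on all dosed patients as a supportive analysis would answer the point.

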7.0 STUDY PATIENTS

7.1 PATIENT DISPOSITION

The OLTP starts with the first dose of OLTP and ends with one of the following: the last scheduled assessment at Visit 12 (Week 16) or early termination (ET) before Visit 12 for patients who do not enter the DBTP; or 1 day before the date of the first dose of DBTP (or the date of the first dose of the DB IP if the last scheduled assessment date in the OLTP is on the date of the first dose of the DBTP) for patients who enter the DBTP.

The DBTP starts with the first day of randomization and ends with the last scheduled assessment at Visit 31 (Week 55) or ET.

The SFU period starts one day after the end of the previous period and ends with the last available assessment. For patients without Visit 32 (Week 57) or Visit 34 (Week 59) assessment, the SFU period would not be derived.

Screen-failure patients (ie, patients screened but not included in the OL Safety Population) and the associated reasons for failure will be tabulated overall for the Screened Population.

The number and percentage of patients in the Screened, OL Safety and OL ITT Populations will be summarized overall and by study center. The number and percentage of patients in the Randomized, DB Safety, and DB ITT Populations will be summarized overall by treatment group and by treatment group and study center.

The number and percentage of patients in the OL Safety Population, who prematurely discontinued from the OLTP, who completed the OLTP, who entered the DBTP, and who entered the SFU period will be summarized overall and by reasons for premature discontinuation as recorded on the OL disposition page of the electronic case report forms (eCRF).

Similarly, the number and percentage of patients in the DB Safety Population who completed the DBTP, who prematurely discontinued from the DBTP, and who entered the SFU period will be summarized overall, by DBTP treatment group and by reasons for premature discontinuation as recorded on the DB disposition page of the eCRF. Patients who relapse during the DBTP will also be summarized as completing the study.

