6.6.7.2 Columbia-Suicide Severity Rating Scale

The C-SSRS is a clinician-rated instrument that reports the severity of both suicidal ideation and behavior. Suicidal ideation is classified on a 5-item scale: 1 (wish to be dead), 2 (nonspecific active suicidal thoughts), 3 (active suicidal ideation with any methods [not plan] without intent to act), 4 (active suicidal ideation with some intent to act, without specific plan), and 5 (active suicidal ideation with specific plan and intent). The C-SSRS also captures information about the intensity of ideation, specifically the frequency, duration, controllability, deterrents, and reasons for the most severe types of ideation. Suicidal behavior is classified on a 5-item scale: 0 (no suicidal behavior), 1 (preparatory acts or behavior), 2 (aborted attempt), 3 (interrupted attempt), and 4 (actual attempt). More than 1 classification can be selected provided they represent separate episodes. For actual attempts only, the actual or potential lethality is classified for the initial, most lethal, and most recent attempts. The C-SSRS will be completed at all study visits. At Visit 1 (Screening), the C-SSRS will be completed for the patient's lifetime history of suicidal ideation and behavior. At all other visits the C-SSRS will be completed for ideation and behavior since the previous visit.

The C-SSRS will be completed by a trained rater with extensive professional training.

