8.4.4 End of OL Period/Randomization Visit (Visit 12)

The following procedures will be carried out at Visit 12:

- Collect samples for UDS; assess blood alcohol concentration via breathalyzer
 - Collect blood samples for serum pregnancy test (women of child-bearing potential only)
- Collect blood samples for clinical laboratory determinations
- Collect blood sample for Hemoglobin A1c
- Review concomitant medications
- Evaluate EPS symptoms (AIMS/BARS/SAS)
- Collect vital signs measurements, including weight and waist circumference (not height)

Perform ECG

- Review and assess AEs and SAEs
- Collect blood for PK evaluation
- Assess CGI-I, PSP, and C-SSRS
- Have patient complete the WPAI-BD QoL questionnaire
- Assess YMRS, MADRS, CGI-S and determine whether randomization criteria (Section 4.6)
 have been met
 - Eligible Patients: Access IWRS to randomize patient and dispense DB IP
 - Patients not meeting randomization criteria are to undergo procedures as for Visit 31/ET and be scheduled to return for 2 safety follow-up visits (Visit 32 and Visit 33)
- Collect IP blister cards and perform drug compliance and accountability

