11.1 ADVERSE EVENTS

Aes will be coded by system organ class and preferred term using the *Medical Dictionary for Regulatory Activities* (MedDRA), Version 21.0 or newer.

An AE will be considered a treatment-emergent adverse event (TEAE) if the AE began or worsened (increased in severity or became serious) on or after the date of the first dose of OL IP. Per eCRF instructions, a new AE record will be created with a new AE onset date for any AE that worsens. Therefore, TEAEs can simply be identified as those Aes with recorded onset date (and time, if known) on or after the date of the first dose of IP.

The number and percentage of patients reporting TEAEs during the OLTP will be tabulated by system organ class and preferred term; by system organ class, preferred term, and severity; and by system organ class, preferred term, and relationship to IP.

The number and percentage of patients reporting TEAEs during the DBTP will be tabulated for each treatment group by system organ class and preferred term; by system organ class, preferred term, and severity; and by system organ class, preferred term, and relationship to IP. The total number and percentage of TEAEs during the DBTP will also be summarized by severity and relationship to IP for each treatment group.

The number and percentage of patients reporting TEAEs during the OL SFU period will be tabulated by system organ class and preferred term for the OL Safety Population. The number and percentage of patients reporting TEAEs during the DB SFU period will be tabulated by system organ class, preferred term, and DB treatment group for the DB Safety Population.

For OLTP, DBTP, or SFU period, if more than 1 AE was coded to the same preferred term for the same patient, the patient will be counted only once for that preferred term using the most severe and most related occurrence for the summarization by severity and by relationship to IP.

An AE that occurs more than 30 days after the date of the last dose of DB IP or occurs after the last SFU visit (whichever comes last) will not be summarized except for Aes related to reported pregnancies. Aes associated with pregnancies reported in the protocol-required timeframe up to approximately 12 weeks following the last dose of DB IP will be summarized.

The number and percentage of patients with common ($\geq 2\%$ of patients in any treatment group) TEAEs will be summarized by preferred term for OLTP and be summarized by preferred term and treatment group for DBTP.

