Clinical laboratory test values will be considered potentially clinically significant (PCS) if they meet either the lower-limit or higher-limit PCS criteria listed in [Table 11.2-1](#). The number and percentage of patients who have PCS postbaseline clinical laboratory values will be tabulated overall for the OLTP, and by treatment group for the DBTP. The percentages will be calculated relative to the number of patients with available non-PCS baseline values and at least 1 postbaseline assessment for the corresponding treatment periods (OLTP or DBTP). The numerator will be the total number of patients with available non-PCS baseline values and at least 1 PCS postbaseline value for the corresponding treatment periods (OLTP or DBTP). A supportive tabular display of patients with PCS postbaseline values will be provided, including the PID number, study center number, and baseline and all postbaseline (including non-PCS) values.

In addition, a tabular display showing all AEs that occurred in patients who had PCS postbaseline clinical laboratory values will be provided.

Potential Hy's Law criteria within a 24-hour window is defined by a post baseline elevation of alanine aminotransferase (ALT) or aspartate aminotransferase (AST) $\geq 3x$ ULN, along with total bilirubin (TBL) $\geq 2x$ ULN and a non-elevated alkaline phosphatase (ALP) $< 2x$ ULN, all based on blood draws collected within a 24-hour period.

Patients who meet the potential Hy's Law criteria during the OLTP will be summarized for the OL Safety Population. Patients who meet the potential Hy's Law criteria from the first dose of DB IP to within 30 days after the last dose of DB IP will be summarized for the DB Safety Population. Supportive tabular displays will also be provided.

[figure not shown]

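### SAP 7.1 lets the open-label and double-blind periods share the randomization day, so some findings from before the first double-blind dose can be counted in the randomized arms, including placebo

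*SAP*

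**What the plan says.** For patients who go on to randomized treatment, SAP 7.1 ends the OLTP "1 day before the date of the first dose of DBTP". A parenthesis replaces this with "the date of the first dose of the DB IP if the last scheduled assessment date in the OLTP is on the date" of that first dose. The next paragraph anchors the other period differently: "The DBTP starts with the first day of randomization and ends with the last scheduled assessment at Visit 31 (Week 55) or ET".

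Protocol 8.4.4 lists the last open-label assessments and, at the same Visit 12, this step: "Eligible Patients: Access IWRS to randomize patient and dispense DB IP".

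Three other rules decide what the period dates do to the safety tables:

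- SAP 11.1 calls an adverse event (AE) treatment-emergent if it began or worsened "on or after the date of the first dose of OL IP". It then tabulates such events during the DBTP by treatment group.
- SAP 11.0 takes the safety baseline before the first open-label dose, unless stated otherwise. A Visit 12 value is therefore postbaseline.
- SAP 11.2 counts patients with potentially clinically significant (PCS) laboratory values who have "at least 1 PCS postbaseline value for the corresponding treatment periods (OLTP or DBTP". SAP 16.3 uses every postbaseline assessment for PCS determinations.

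For the C-SSRS, Protocol 6.6.7.2 sets the recall period after screening: "At all other visits the C-SSRS will be completed for ideation and behavior since the previous visit".

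**The concern.** The treatment-emergent definition is anchored to the first open-label dose, so it cannot separate open-label onset from double-blind onset. Only the period dates assign an event to a randomized arm. If those dates overlap, an AE that began on open-label cariprazine 3.0 mg/d on the randomization day, before any DB capsule, meets the definition for both periods. It can then appear under placebo.

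The same applies to counts that accept any postbaseline value in the period. A Visit 12 measurement reflects open-label treatment but is dated on a day that belongs to the DBTP. The Visit 12 C-SSRS looks back over about two open-label weeks.

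At stake is the by-arm DB safety comparison. Randomization spreads pre-dose findings evenly in expectation. They therefore raise the rate in every arm, and any ratio a reader forms from the table is pulled toward 1.

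**Working it through.** The documents state no figure on this point to reproduce. The check is one of date logic and schedule counts.

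**Step 1. Overlap.** Let A be the date of the last open-label assessment (Visit 12), R the randomization date and D the first DB dose date. From SAP 7.1:

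- OLTP end = D if D = A, otherwise D − 1
- DBTP start = R
- Overlap in days = max(0, OLTP end − R + 1)

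Setting A = day 0:

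| R | D | OLTP end | DBTP start | Overlap (days) |
|---|---|---|---|---|
| 0 | 0 | 0 | 0 | 1 |
| 0 | 1 | 0 | 0 | 1 |
| 0 | 2 | 1 | 0 | 2 |
| 0 | 3 | 2 | 0 | 3 |
| 1 | 1 | 0 | 1 | 0 |
| 1 | 2 | 1 | 1 | 1 |

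The first two rows are the ordinary case under Protocol 8.4.4: assessment and randomization on one day, first DB dose that day or the next.

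**Step 2. Which tables the overlap reaches.** On the literal wording:

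- AEs with onset on the overlap day(s) (SAP 11.1).
- PCS laboratory, vital-sign and ECG counts (SAP 11.2, 11.3, 11.4).
- Shift to the highest hypertension category during the DBTP (SAP 11.3).
- Treatment-emergent parkinsonism and akathisia, defined on any postbaseline score (SAP 11.5.3).
- C-SSRS ideation and behavior by treatment group (SAP 11.5.2).

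Analyses with their own anchor are the DB part of the potential Hy's Law summary (SAP 11.2), DB concomitant medication and DB efficacy baseline (SAP 8.0), and the derived DB weeks used for by-visit summaries (SAP 10.0, applied to safety in 11.0). All of these use the first DB dose. The primary endpoint runs from randomization (SAP 10.1) and needs no change.

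**Step 3. Exposure by assessment.** From Protocol Table 1, for a patient who completes the DBTP, Visit 12's share of the scheduled assessments if it is dated in the DBTP would be:

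| Assessment | Scheduled in DBTP | With Visit 12 | Visit 12 share |
|---|---|---|---|
| ECG | 1 (Visit 31) | 2 | 1/2 = 50% |
| Clinical laboratory | 3 (Visits 18, 24, 31) | 4 | 1/4 = 25% |
| EPS scales | 10 (even visits 14–30, and 31) | 11 | 1/11 = 9% |
| Vital signs | 19 (Visits 13–31) | 20 | 1/20 = 5% |
| C-SSRS | 19 (Visits 13–31) | 20 | 1/20 = 5% |

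These are shares of the schedule and do not estimate bias.

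**Step 4. Would moving the start date be enough?** Put DBTP start = D and keep the OLTP end rule. For D = 1, 2 or 3 the overlap is 0. For D = 0 it is still 1 day, because the parenthesis keeps the OLTP open through that date. A same-day rule is needed as well.

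**The case against.** The strongest reply is that the SAP nowhere says Visit 12 findings count in the DB arms, and much of it points the other way. SAP 7.1 treats Visit 12 as the last OLTP assessment for patients who are not randomized. Table 4-2 lists it under the open-label period as End of OL. SAP 12.0 assigns Week 16 to the OLTP. SAP 16.2 has a special rule sending late open-label ophthalmologic examinations to DB windows, which suggests that on-time examinations stay open-label. The window tables in SAP 16.1 are not shown and may settle the by-visit summaries. This stands for by-visit summaries: no double counting can be shown there. It does not settle AEs, which have no visit label, or the any-postbaseline counts, where SAP 16.3 takes all assessments and the period dates decide.

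Second, the consequences can be overstated. Safety is descriptive and no AE risk ratio is planned. The open-label and DB tables have separate denominators. A same-day AE may follow the first DB dose. All of this is correct and limits the importance of the point. An AE that began before that dose is still placed in a randomized arm.

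Third, the effect may be too small to change any conclusion. That is probably right for AEs. A reader might try to size it by assuming 1 to 3 AE onsets per patient over 12 to 16 open-label weeks, spread evenly: 1/112 = 0.9% to 3/84 = 3.6% of patients per day, or 3.4 to 13.5 events among 378. The documents give no AE rate, so this range cannot be relied on. Randomized patients have also been selected for tolerating 3.0 mg/d, so an average open-label rate may not describe their last open-label day. Onsets recorded at visits could push the figure up.

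**Conclusion.** The period definitions in SAP 7.1 overlap for a patient assessed and randomized at the same Visit 12, and the legible text has no tie-break. This is a stated rule that assigns some data to two periods. It looks unintended: the same section starts safety follow-up the day after the previous period ends, and several other analyses already start at the first DB dose.

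Three stronger readings are tempting, and the documents do not support them:

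- That open-label AEs in general enter the randomized arms. Only onsets on the overlap day(s) do.
- That the periods overlap for every patient. There is no overlap when randomization and first dose both fall the day after the last open-label assessment.
- That all Visit 12 findings are shown to be counted twice. For any-postbaseline counts this follows only from the literal wording; for by-visit summaries it is unconfirmed.

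The number of AEs affected is unknown and likely small. The clearest exposure is the DB ECG count, where Visit 12 would supply one of two scheduled tracings. The analyses with their own anchor, the primary relapse analysis among them, are not shown to be affected. The conclusion assumes that Visit 12 and randomization usually fall on one date and that programming follows SAP 7.1 as written. The definitions should be corrected before unblinding.

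**What to change.** In SAP 7.1, for safety analyses:

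1. Start the DBTP at the first DB dose and end the OLTP just before it.
2. Assign all Visit 12 assessments made before that dose to the OLTP only.
3. Assign an AE starting on the first-DB-dose date by onset time relative to the dose. State one default, the same for all arms, for when the time is unknown.

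The start date and the same-day rules are needed together (Step 4 of the working). Keep randomization as time zero for relapse.

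The cost is a few lines of SAP text and a date comparison in programming. SAP 11.1 already refers to onset time where known. The downside is that a few same-day AEs will depend on the tie rule.
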